ALT	alanine aminotransferase/glutamic pyruvic transaminase/GPT
AST	aspartate aminotransferase/glutamic oxaloacetic transaminase/GOT
AV	atrioventricular
bpm	beats per minute
BUN	blood urea nitrogen
BP	blood pressure
CRC	Central Reading Center
CRF	Case Report/Record Form
CSF	cerebrospinal fluid
CNS	central nervous system
CRO	Contract Research Organization
DMD	disease modifying drugs
DS&E	Drug Safety and Epidemiology
EAE	experimental autoimmune encephalomyelitis
ECG	Electrocardiogram
EDC	electronic data capture
EDSS	expanded disability status scale
FA	fluorescein angiography
FDA	First dose administration
GCLT	ganglion cell layer thickness
GGT	gamma-glutamyl-transferase
HCG	human chorionic gonadotropin
IB	investigator's brochure
ICH	International Conference on Harmonization
IEC	Independent Ethics Committee
IFN	interferon
IRB	Institutional Review Board
i.m.	intramuscular(ly)
IUD	intrauterine device
i.v.	intravenous(ly)
LN	lymph node
MRI	magnetic resonance imaging

MS	multiple sclerosis
██████	██
o.d.	omnia die/once a day
OCT	optic coherence tomography
ON	optic neuritis
██████	████████████████████
██████	████████████████████
PML	progressive multifocal leukoencephalopathy
PCR	polymerase chain reaction
p.o.	per os/by mouth/orally
PPMS	primary progressive multiple sclerosis
██████	██
██████	████████████████████
RBC	red blood cell
REB	Research Ethics Board
RMP	risk management plan
RNFL(T)	retinal nerve fiber layer (thickness)
RRMS	relapsing remitting multiple sclerosis
SAE	serious adverse event
s.c.	subcutaneously
██████	██
SmPC	Summary of Product Characteristics
SPMS	secondary progressive multiple sclerosis
TMV	total macular volume
ULN	upper limit of normal range
VEP	visual evoked potential
WBC	white blood cell count
WHO	World Health Organization

Amendment 1

Amendment Rationale

The protocol is being amended to implement an update to the Gilenya® (fingolimod) label in the EU approved by the Committee for Medicinal Products for Human Use (CHMP), as well as in Switzerland as approved by Swissmedic.

The updates to the label provide refined guidance on when existing first dose monitoring procedures should be repeated.

The updates were submitted to both Health Authorities as a Type II Variation by Novartis. These recommendations are already included in the US Prescribing Information (PI) and are not related to any new safety reports.

In agreement with the FDA, both EMA and Swissmedic confirmed the positive benefit-risk profile for Gilenya when used in accordance with updated labels, which were announced earlier this year.

Novartis informed healthcare professionals in the European Union of these recommendations via a Direct Healthcare Professional Communication (DHPC) by January 11, 2013, in Switzerland Physicians were informed via a DHPC Letter on January 22nd 2013.

Changes to the protocol

- In patients who are re-initiated after a certain treatment interruption a repetition of first-dose-monitoring strategy is necessary.
- In patients who require pharmacological intervention during the first dose monitoring and are monitored overnight in a medical facility the first dose monitoring should be repeated after the second dose of fingolimod (For EU only; already implemented in Swiss label).

Additional changes to the protocol

- One center in Switzerland is added
- Section 7.6.4 “Pregnancy and assessments of fertility” is updated

Changes to specific sections of the protocol are shown in the track changes version of the protocol using ~~strike through red font~~ for deletions and red underlined for insertions.

A copy of this amended protocol will be sent to the Institutional Review Board (IRBs)/Independent Ethics Committee (IECs) and Health Authorities. The changes described in this amended protocol require IRB/IEC approval prior to implementation.

The protocol synopsis has been updated accordingly. In addition, as the changes herein affect the Informed Consent, a revised Informed Consent will also be submitted for approval to IRB/IEC.

Amendment 2

Amendment Rationale

The protocol is being amended to further define blood biomarker sampling and to define the period of one month as 28 days. Furthermore, the specifications for contraception and for elevated liver function tests are adjusted and some inconsistencies within the protocol are corrected.

Changes to the protocol

- Section 3.3, 7.5.5, and 10.5.7: wording has been adjusted to further define blood biomarker sampling. A subset of 50 patients was determined.
- Section 5.1, 6.5 and 7: One month was defined as 28 days and visit 2 is defined as inclusion date (section 5.1)
- Section 6.5 and Appendix 7: wording has been adjusted corresponding to the wording of the SmPC; study drug has to be discontinued if liver function tests are repeatedly >5x ULN.
- Section 7.6.3 and Appendix 3: some corrections were made to adjust inconsistencies within the protocol and to further define laboratory evaluations.
- Section 7.6.4: wording has been adjusted to permit also secondary and other forms of contraception (Pearl index <1).

Changes to specific sections of the protocol are shown in the track changes version of the protocol using ~~strike through red font~~ for deletions and red underlined for insertions.

A copy of this amended protocol will be sent to the Institutional Review Board (IRBs)/Independent Ethics Committee (IECs) and Health Authorities. The changes described in this amended protocol require IRB/IEC approval prior to implementation.

In addition, as the changes herein affect the Informed Consent, a revised Informed Consent will also be submitted for approval to IRB/IEC.

Amendment 3

Amendment Rationale

The protocol is being amended to remove blood biomarker sampling from the protocol.

Changes to the protocol

- Section 1, 3.3, 7, 7.5.5, 10.5.7, 11, and Appendix 2: Blood biomarker sampling was completely removed and wording has been adjusted.
- Section 9.3: The responsible person for the OCT Quality Control, Dr. [REDACTED] has been added

Changes to specific sections of the protocol are shown in the track changes version of the protocol using ~~strike through red font~~ for deletions and red underlined for insertions.

A copy of this amended protocol will be sent to the Institutional Review Board (IRBs)/Independent Ethics Committee (IECs) and Health Authorities. The changes described in this amended protocol require IRB/IEC approval prior to implementation.

In addition, as the changes herein affect the Informed Consent, a revised Informed Consent will also be submitted for approval to IRB/IEC.

Amendment 4

Amendment Rationale

The protocol is being amended to clarify the minimum pre-treatment with fingolimod as 28 days and to adapt the visit schedule to the recommended visit schedule in the fingolimod product information. The fingolimod product information recommends visits every 3 months of treatment. Therefore a month during the observational period of the study is defined as 28-31 days depending on the actual length of the respective month. The definition of one month as 28 days is removed.

Changes to the protocol

- Section 5.1 and table 7-1 are changed according to the amendment rationale.

Changes to specific sections of the protocol are shown in the track changes version of the protocol using ~~strike through red font~~ for deletions and red underlined for insertions.

All changes in the protocol are classified as non-substantial. Therefore an Institutional Review Board (IRBs)/Independent Ethics Committee (IECs) approval prior to implementation is not necessary.

Glossary of terms

Assessment	A procedure used to generate data required by the study
Enrollment	Point/time of patient entry into the study; the point at which informed consent must be obtained (i.e., prior to starting any of the procedures described in the protocol)
Patient number	A number assigned to each patient who enrolls in the study; when combined with the center number, a unique identifier for each patient in the study is created.
Phase	A major subdivision of the study timeline; begins and ends with major study milestones such as enrollment, randomization, completion of treatment, etc.
Premature patient withdrawal	Point/time when the patient exits from the study prior to the planned completion of all study assessments; at this time no further assessments are planned
Stop study participation	Point/time at which patient came in for a final evaluation
Variable	Information used in the data analysis; derived directly or indirectly from data collected using specified assessments at specified timepoints

1 Background

Multiple Sclerosis (MS) is a chronic, demyelinating, immune-mediated disease of the central nervous system affecting about 2.3 times as many women as men (Alonso & Hernan, 2008). With regard to disease pathogenesis, MS is characterized by inflammation and destruction of myelin and axons (Trapp et al., 1998, Sospedra & Martin, 2005). Typically recurrent acute episodes (relapses) of neurological symptoms, which are followed by a complete or partial recovery, can be observed during the relapsing remitting multiple sclerosis (RRMS) disease course (about 85% of patients at diagnosis). Approximately 50% of these patients progress to secondary progressive MS (SPMS) within 10 years, 90% within 25 years. In these SPMS patients a less inflammatory and more neurodegenerative course of disease appears to take precedence. Apart from these initially relapsing forms of MS 10-15% of patients present with primary progressive MS (PPMS), which is characterized by steady deterioration of impairment without prior experience of relapses (Keegan & Noseworthy, 2002).

The driving force of disability in MS is axonal loss. In MS, axonal loss seems to be associated with thinning of the retinal nerve fiber layer (RNFL). The RNFL contains ganglion cell axons that give rise to the optic nerve. Myelination of these fibers begins behind the eye, at the level of the lamina cribrosa (Frohman et al. 2008). The RNFL represents a unique region of the central nervous system because it lacks myelin and thus, allows for direct imaging of axons. It has therefore emerged as a highly interesting potential marker for the evaluation of axonal loss in MS. The thickness of the RNFL itself and the amount of change that may occur, however, are both very small (few microns) making a reliable assessment of RNFL thickness change challenging. Currently, optical coherence tomography (OCT) is the most accurate method to measure RNFL thickness.

Optical coherence tomography (OCT) is a validated, sensitive, non-invasive technique that uses low-coherence interferometry to obtain cross-sectional images of the retina. Commercially available OCT machines show good reproducibility of the measurement of RNFL thickness (Serbecic et al, 2010; Syc et al, 2010; Wu et al, 2010). With the latest technical improvements such as higher resolution and dual laser beam to overcome eye movements these instruments may have a high clinical utility in predicting MS disease course and determining treatment response.

In MS, visible RNFL thinning by OCT may be seen when inflammation causes degeneration of axons within the optic nerve, e.g. as a result of optic neuritis (ON), a common manifestation in MS. However, RNFL thickness is reduced even in the absence of acute ON, making RNFL atrophy a potential structural biomarker of axonal injury or loss in the afferent visual pathway (Frohman et al, 2008; Barkhof et al, 2009; Talman et al, 2010). Cross-sectional studies in patients with MS have shown that RNFL thickness by OCT correlates with clinically relevant measures of disability like brain atrophy (Petzold et al, 2010) and cognitive decline (Toledo et al, 2008). Limited available longitudinal OCT data indicate that progressive RNFL thinning occurs over time in the eyes of MS patients and that this may correlate with change in clinically relevant parameters (Costello et al, 2009; Talman et al, 2010). A recent study in 299 MS patients with a mean follow-up of 18 months showed that progressive RNFL thinning observed over time (in eyes with and without prior history of ON) was associated with significant visual loss (Talman et al, 2010). Further studies are needed to evaluate if changes in RNFL are correlated also with global measures of disability in more detail (e.g. EDSS, patient reported outcomes, etc.).

To address this and to describe the change in RNFL thickness over time a global study is planned that includes RRMS patients (either untreated or treated with any approved MS disease modifying therapy) and a group of reference subjects (without neurologic or ophthalmic disease). Since the global study is not powered to particularly detect changes under fingolimod treatment – fingolimod is not even approved in all participating countries – the present study focuses on this subpopulation.

Fingolimod (FTY720; Gilenya[®]) is an oral, once daily disease modifying drug which has been approved for the treatment of relapsing MS in the US (on 21-Sep-2010), Europe (on 17-03-2011) and other countries.

Pharmacologically, fingolimod targets a novel class of G protein-coupled receptors (GPCRs) which bind the pleiotropic sphingolipid mediator sphingosine 1-phosphate (S1P) and acts in large part by down-modulating S1P/S1P receptor responses in the immune- and the central nervous systems. It causes a reversible sequestration of a proportion of CD4+ and CD8+ positive T-cells and B-cells from blood and spleen into lymph nodes (LNs) and Peyer's patches, apparently without affecting many of the functional properties of these cells. Under normal circumstances, T-cells selectively require S1P1 activation for emigration from the thymus, and both T- and B-cells require this receptor to egress from peripheral lymphoid organs. FTY720-P acts as a super agonist of the S1P1 receptor on lymphocytes, inducing its uncoupling/internalization. The internalization of S1P1 renders these cells unresponsive to S1P, depriving them of the obligatory signal to egress from lymphoid organs and recirculate to peripheral inflammatory tissues. As a consequence, autoaggressive T-cells remain trapped in the lymphoid system, i.e. in the autoantigen-draining cervical LNs in experimental autoimmune encephalomyelitis (EAE)/MS, and this reduces their recirculation to the CNS and abrogates central inflammation.

Fingolimod has shown clinical efficacy in several stages of MS. There is indirect evidence of neuroprotection by this compound due to its unique mode of action. This study should elucidate what changes in RNFLT (retinal nerve fiber layer thickness) occur using late-stage spectral domain OCT during oral treatment with fingolimod. In parallel, investigations will include the safety of fingolimod and other OCT parameters like changes in total macular volume or papillomacular bundles.

In summary, the present study will provide important longitudinal data towards the development of the RNFL under fingolimod treatment as assessed by OCT as an outcome measure in MS over a period of 36 months.

2 Study purpose

This is a 3-year, prospective, multi-center, open-label study to describe the long term changes of optical coherence tomography (OCT) parameters in RRMS patients under treatment with Fingolimod. It is designed to longitudinally study the degeneration of retinal axons by measuring change in RNFL thickness by latest OCT-technology. Correlations of OCT findings with available MRI data and clinical findings may enhance our understanding of the relationship between CNS inflammation, tissue injury, regeneration and neurological deficit in the context of fingolimod therapy.

3 Objectives

3.1 Primary objective

To evaluate the change in average RNFL thickness (RNFLT) in RRMS patients treated with fingolimod over 36 months as assessed by OCT

3.2 Secondary objectives

To evaluate the change in average RNFLT under fingolimod therapy from baseline to months 12 and 24 as assessed by OCT

[figure not shown]
To evaluate change in quadrant RNFLT under fingolimod therapy from baseline to months 12, 24 and 36

To evaluate changes in total macular volume (TMV) under fingolimod therapy from baseline to months 12, 24 and 36

To evaluate changes in ganglion cell layer thickness (GCLT) under fingolimod therapy from baseline to months 12, 24 and 36

To compare changes in OCT parameters between eyes with and without history of optic neuritis and between right and left eye

[figure not shown]
To evaluate safety and tolerability of fingolimod in MS patients followed for up to 36 months and specifically to determine the frequency of macular edema under treatment with oral fingolimod in this patient population

4 Study design

This is a multi-center, open-label study in RRMS patients treated with fingolimod. After signing the informed consent, patients will enter a Screening Phase (day -28 to day 0) before starting the study at Baseline (day 0), followed by a 36-month longitudinal data collection phase (see Figure 4-1). Eligibility will be determined at Screening. OCT and other assessments will be performed according to the schedule in Table 7-1.

Figure 4-1 Study outline

5 Population

In this study approximately 100 patients with MS are expected to be enrolled in Germany and Switzerland.

The investigator must ensure that all patients who meet the following inclusion and do not fulfill any of the exclusion criteria are offered enrollment in the study. No additional exclusion parameters can be applied by the investigator, in order that the study population will be representative of all eligible patients.

Patients who drop out after baseline during the longitudinal phase will not be replaced.

The study is planned to be conducted at approximately 10 sites in Germany and approximately 1 site in Switzerland.

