10.5 Analysis of secondary [REDACTED] objectives

10.5.1 Secondary [REDACTED] outcomes

Secondary endpoints like changes in quadrant RNFLT, changes in total macular volume (TMV), and changes in ganglion cell layer thickness (GCLT) from baseline to months 12, 24, and 36 will be evaluated with a paired t-test or Wilcoxon signed-rank test, as appropriate.

Changes in OCT parameters between eyes with and without history of optic neuritis will be evaluated with a paired t-test or Wilcoxon signed-rank test, as appropriate.

[REDACTED]

Additionally, means, standard deviations, median, minimum and maximum will be presented for each visit, as will be the change from baseline. These descriptive statistics will also be presented for the primary endpoint.

For all other [REDACTED] endpoints summary statistics will be presented. Summary statistics will include n (number of observations), mean, standard deviation, median, minimum and maximum values at each visit, as well as the change.

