1.2 Study objectives and endpoints

The primary objective is to evaluate the change in average RNFL thickness (RNFLT) in RRMS patients treated with fingolimod over 36 months as assessed by OCT. The average RNFL thickness following OCT assessment will be calculated for the left and right eye per visit and per patient. The following table describe the objectives and endpoints:

	Objective	Endpoint
Primary	To evaluate the change in average RNFL thickness (RNFLT) in RRMS patients treated with fingolimod over 36 months as assessed by OCT	Absolute Difference in mean RNFLT from baseline (BL) to M36 (or last values in case of missing data) in the full analysis set (FAS). Mean RNFLT is the average of valid measurements of right and left eye. Sensitivity analyses are performed with the Per-Protocol Set (PPS) and for relative change (M36/BL)
Secondary	To compare changes in OCT parameters between eyes with and without history of optic neuritis	Absolute Difference in RNFLT from baseline (BL) to M36 (or last values in case of missing data) in the full analysis set (FAS) for: - eyes with versus without optic neuritis
Secondary	To evaluate the change in average RNFLT under fingolimod therapy from	Absolute Difference and ratios in average RNFLT from baseline (BL) to M12 respectively M24 (or last values in case of missing data) in the full analysis set (FAS).

	Objective	Endpoint
	baseline to months 12 and 24 as assessed by OCT	
Secondary	To evaluate change in quadrant RNFLT under fingolimod therapy from baseline to months 12, 24 and 36	
Absolute Difference and ratios in average quadrant RNFLT from baseline (BL) to M12, resp. M24 resp. M36 (or last values in case of missing data) in the full analysis set (FAS).
 
Quadrant RNFLT are:
 
 - Nasal-inferior - Nasal-superior - Temporal.inferior - Temporal-superior
Secondary	To evaluate changes in total macular volume (TMV) under fingolimod therapy from baseline to months 12, 24 and 36	Absolute Difference and ratios in average TMV from baseline (BL) to M12, resp. M24 resp. M36 (or last values in case of missing data) in the full analysis set (FAS).
Secondary	To evaluate changes in ganglion cell layer thickness (GCLT) under fingolimod therapy from baseline to months 12, 24 and 36	Absolute Difference and ratios in average GCLT from baseline (BL) to M12, resp. M24 resp. M36 (or last values in case of missing data) in the full analysis set (FAS).

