2.5.4 Supportive analyses

A comparison for eyes with versus without optic neuritis is done by a mixed model including the subject as random factor. LSMMeans for RNFLT in eyes with versus without optic neuritis are displayed as well as the difference including p-value.

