2.14 Interim analysis

Not applicable.

3 Sample size calculation

Published data varies widely as to the average thinning of RNFL in MS patients and no data is available on patients treated with Fingolimod. As this is an explorative study to get a better understanding of RNFL thinning in RRMS treated with Fingolimod we will take a representative sample of approximately 100 patients with RRMS who are stable on Fingolimod

4 Change to protocol specified analyses

[figure not shown]
The change in ganglion cell layer thickness (GCLT) was defined as secondary endpoint, but OCT measured the ganglion cell inner plexiform layer (GCIP). This was done because both layers are not clearly separable by OCT. The volume of GCIP is declared as usual parameter.

5 Appendix

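### The visible SAP analyses only part of a protocol secondary objective (RNFLT by optic-neuritis history), with no other OCT parameter and no right-versus-left contrast, and does not list the narrowing as a change

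*Protocol*

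**What the plan says.** Protocol 3.2 names four types of OCT parameter among its secondary objectives or in the primary one they extend: average RNFLT, quadrant RNFLT, TMV and GCLT. A further objective in the same section sets two eye-level contrasts: "To compare changes in OCT parameters between eyes with and without history of optic neuritis and between right and left eye".

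Protocol 10.5.1 gives a method for the first contrast: "Changes in OCT parameters between eyes with and without history of optic neuritis will be evaluated with a paired t-test", with a Wilcoxon signed-rank test as the alternative. The outcome is again OCT parameters in the plural. The visible text of 10.5.1 gives no method for right versus left.

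The objectives table in SAP 1.2 restates the objective as "To compare changes in OCT parameters between eyes with and without history of optic neuritis" and stops there. The endpoint beside it is "Absolute Difference in RNFLT from baseline (BL) to M36" (or the last value), and the only contrast listed is "eyes with versus without optic neuritis".

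SAP 2.5.4 gives the method: "A comparison for eyes with versus without optic neuritis is done by a mixed model including the subject as random factor". It also gives the output: "LSMMeans for RNFLT in eyes with versus without optic neuritis are displayed", with their difference and a p-value. SAP 5.3.2 supplies code with change in RNFLT as the outcome and `opt_neur` as the only fixed effect.

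SAP section 4, on changes to the protocol-specified analyses, visibly holds one item. It begins "The change in ganglion cell layer thickness (GCLT) was defined as secondary endpoint" and explains that GCIP was measured instead.

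**The concern.** A secondary objective should lead to a defined result. Here the objective covers several parameters and two contrasts, while the visible SAP gives one parameter and one contrast. An analyst who follows the SAP will not report whether eyes with past optic neuritis differ in macular volume, ganglion-cell layer or quadrant thickness change, nor whether the two sides differ on any measure. The data will exist, since Protocol 7.3 has both eyes scanned at baseline and at Visits 3 to 7.

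Traceability is also at stake. Section 4 is where a reader looks for departures from the protocol. Because it records one change, a reader will take the rest of the protocol analysis to stand. A later report without these comparisons would leave it unclear whether they were dropped by plan.

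**Working it through.** The plan gives no figure to reproduce, so the check is a comparison of texts followed by a count.

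**Step 1. The places side by side.**

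| Place | Parameters | Optic-neuritis contrast | Right/left contrast | Method |
|---|---|---|---|---|
| Protocol 3.2 | OCT parameters, plural | yes | yes | not stated there |
| Protocol 10.5.1 (visible) | OCT parameters, plural | yes | none visible | paired t-test or Wilcoxon |
| SAP 1.2, row for this objective | RNFLT | yes | omitted | not stated there |
| SAP 2.5.4 | RNFLT | yes | none | mixed model, random subject |
| SAP 5.3.2 | RNFLT | yes | no side term | same model, as code |
| SAP 4 (visible) | GCLT to GCIP only | not mentioned | not mentioned | change not mentioned |

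**Step 2. Coverage count.** I assume that OCT parameters means the four types named in Protocol 3.2.
- By type: 4 parameters × 2 contrasts = 8 comparisons, of which the visible SAP specifies 1.
- With the four quadrants counted separately: 1 average RNFLT + 4 quadrants + 1 TMV + 1 GCLT/GCIP = 7 measures. Then 7 × 2 = 14 comparisons, of which the visible SAP specifies 1.
- By contrast: optic-neuritis history is covered for 1 of 4 types (1 of 7 measures), and side for 0 of 4 (0 of 7).

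**Step 3. Does a general clause fill the gap?** SAP 2.7.2 says that secondary endpoints are analysed much like the primary one. The primary variable in SAP 2.5.1 is a patient-level mean over the valid eyes, and SAP 1.2 also words the quadrant, TMV and GCLT endpoints as averages. Once two eyes are averaged, the value carries neither an eye-level optic-neuritis flag nor a side. Only SAP 5.3.2 sets averaging aside and builds an eye-level dataset, and it does so for RNFLT alone.

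**Step 4. Does the one specified comparison run?** In the SAP 5.3.2 code the CLASS statement holds `patno` and `opt_neur`, and the MODEL statement holds `opt_neur`. The `lsmeans` statement asks for `krank`, which is in neither. As written, the code does not deliver the least-squares means promised in SAP 2.5.4, so it must be corrected before it is extended to other outcomes.

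**The case against.** **Parts of the text cannot be seen.** A redacted block follows the optic-neuritis sentence in Protocol 10.5.1. The list in SAP 2.7.1 shows a single bullet although SAP 1.2 has more secondary endpoints, and a missing figure stands under the heading of SAP section 4. This stands as a limit. A reader might infer that no right/left analysis exists anywhere in the plan, or that section 4 certainly contains one item; the documents do not support either. The point rests on the SAP 1.2 row, which reads as complete, and on 2.5.4 and 5.3.2, which agree with it.

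**The right/left gap does not start in the SAP.** Visible Protocol 10.5.1 gives no analysis for it, so strictly there may be no protocol-specified analysis for section 4 to report as changed. This also stands. The argument for listing a change is firmer for the restriction to RNFLT and for the change of method, because Protocol 10.5.1 specifies both the plural parameters and the paired test.

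**SAP 2.7.2 may carry the model over.** The optic-neuritis model sits within the primary-objective section, so the cross-reference could be stretched to cover it. Step 3 shows why this reading is weak: the other endpoints are defined as averages, and the eye-level outcome named is RNFLT.

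**The primary endpoint is not put at risk.** A reader might infer that a side difference would make patients with one valid eye non-comparable. The endpoint is a change. If a side has a constant offset d, the change within that eye is (T36 + d) − (T0 + d) = T36 − T0, and d drops out. Only a side difference in the rate of change would matter, and the documents give no reason to expect one.

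**The study is exploratory.** SAP 2.5.2 and 2.7.2 test no hypothesis, SAP 2.7.2 treats p-values as descriptive, and SAP 2.6 names no key secondary objective. That limits the weight of the point. It does not remove it, since a descriptive study still has to report what it set out to describe.

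**Conclusion.** The point holds on the visible text. The SAP specifies 1 of 8 comparisons set by the objective when parameters are counted by type, or 1 of 14 when quadrants are counted separately. It specifies none by side. Visible section 4 records neither the restriction to RNFLT nor the move to a mixed model.

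The count depends on reading OCT parameters as the four types in Protocol 3.2, since the term is not defined. The Protocol background also mentions papillomacular bundles, which neither count includes. The finding of absence covers the visible text only.

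The consequence is an incomplete secondary objective and an incomplete record of changes. The primary result is unaffected. The documents do not show selective reporting, and the mixed model is not a fault in itself: it can use every eye, whereas a within-patient pairing of affected and unaffected eyes needs one of each. What is missing is its entry as a change.

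**What to change.** 1. In SAP 5.3.2, replace `krank` with `opt_neur` in the `lsmeans` statement.
2. Add eye side to the CLASS, MODEL and `lsmeans` statements, keeping patient as the random effect, so that both contrasts come from one model.
3. Run that model on eye-level change in average RNFLT, each quadrant RNFLT, TMV and GCIP. Report each difference with a 95% CI, labelled descriptive.
4. Restore the right/left wording in the SAP 1.2 row and name all the parameters in its endpoint.
5. In SAP section 4, list the move from paired t-test or Wilcoxon to a mixed model. If any parameter or the side contrast is left out on purpose, list that too, with the reason.

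No new data are needed. The cost is a few more descriptive table rows and more unadjusted comparisons, which should be read as estimates and not as tests.
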